2.2.2 Preclinical Efficacy of CB-5339: xenograft studies

The preclinical efficacy of CB-5339 was also demonstrated in A549 human lung adenocarcinoma, AMO-1 multiple myeloma, and RPMI8226 multiple myeloma xenograft models. Optimal doses of first-generation CB-5083 determined from previous studies were included as controls.

A549 lung adenocarcinoma xenografts (Cleave Pharmacology Report 02-00016)

The efficacy of 3 different CB-5339 dosing regimens were evaluated over an 18-day period in female SCID beige mice bearing human A549 lung adenocarcinoma xenografts. The dosing regimens for CB-5339 were QD4/3 off doses of 100 mg/kg (Group 2), bi-weekly (BIW) doses of 150 mg/kg, and once-weekly dose (1/W) doses of 225 mg/kg. Other animals received QD4/3 off doses of 55 mg/kg CB-5083 (optimal dose from previous studies).

[figure not shown]

Figure 5: The strongest antitumor activity was seen in group 2: QD4/3 off dosing of 100 mg/kg resulted in a tumor growth inhibition (TGI) of 61%. This dosing regimen was generally tolerated throughout the study with 7.0% mean body weight loss on day 2 and a single drug-related death within the study group. QD4/3 off administration of 55 mg/kg

CB-5083 resulted in a 33% TGI.

AMO-1 multiple myeloma xenografts (Cleave Pharmacology Report 02-00015)

The efficacy of 6 different CB-5339 dosing regimens were evaluated over a 12-day period in female SCID Beige mice bearing human AMO-1 multiple myeloma xenograft tumors. The dosing regimens for CB-5339 were 1/W doses of 225 and 275 mg/kg (Groups 2 and 3, respectively), BIW doses of 150 and 200 mg/kg, and QD4/3 off doses of 80 or 100 mg/kg. Other animals received QD4/3 off doses of 60 mg/kg CB-5083 (optimal dose in previously reported experiments)

[figure not shown]

Figure 6: Very strong antitumor activity was seen for groups 2 and 3; weekly dosing of 225 and 275 mg/kg resulted in TGI of 102% and 112%, respectively. This strong antitumor response observed with the 225 mg/kg QD1 dosing regimen was accompanied with a 16% mean regression on day 12, as well as 4/7 partial regressions and 3/7 complete regressions within the study group. Administration of 225 mg/kg CB-5339 was generally tolerated, promoting a -4.8% mean body weight loss on day 4. In comparison, the 275 mg/kg 1/W dosing regimen was more efficacious with an 84% mean regression on day 12. However, the activity observed at 275 mg/kg 1/W should be

[figure not shown]
mitigated by the 3/8 drug-related deaths that occurred within this study group, suggesting that greater toxicity is associated with this dosing regimen. Strong antitumor activity was also seen for the 200 mg/kg BIW dosing regimen, which resulted in a TGI of 109%.

This response was accompanied with a 64% mean regression on day 12, as well as 2/7 partial

regression and 4/7 complete regression. BIW administration of 200 mg/kg CB-5339 was generally tolerated, promoting a -4.1% mean body weight loss on day 8. Of note, treatment with CB-5083 resulted in a TGI of 110% and a 68% mean regression on day 12, but the drug was not well tolerated in these experiments; CB-5083 can be highly active in the AMO-1 model and the activity observed here is comparable to that previously reported. In conclusion, a variety of CB-5339 dosing regimens showed strong antitumor activity against the human MM AMO-1 xenograft model.

RPMI8226 multiple myeloma xenografts (Cleave Pharmacology Report 02-00014)

The efficacy of 2 different doses of CB-5339 were evaluated over an 18-day period in female SCID Beige mice bearing human RPMI8226 multiple myeloma xenograft tumors. The dosing regimens were QD4/3 off doses of 100 and 125 mg/kg CB-5339 (Groups 2 and 3, respectively); other animals received QD4/3 off doses of 60 mg/kg CB-5083 (optimal dose).

TGI and a 42% mean regression on day 18. This strong antitumor response was accompanied with 5/8 PR within the study group.

In conclusion, a QD4/3 off dosing regimen of 100 mg/kg of CB-5339, showed strong antitumor activity against a human MM RPMI8226 xenograft model.

Figure 7: Antitumor activity was seen for CB-5339 groups 2 and 3, with a 94% and 119% TGI, respectively. The antitumor response observed with the 100 mg/kg QD4/3 off dosing regimen was accompanied with 1/8 partial regressions within the study group. QD3/4 off administration of 100 mg/kg of CB-5339 was generally tolerated. In comparison, the 125 mg/kg QD4/3 off dosing regimen resulted in a 26% mean regression on day 18, as well as 3/7 PR within the study group. However, 1/7 drug related deaths and significant (>10%) weight losses were observed days 6-10 within this study group. CB-5083 resulted in a 129%

2.2.3 Pharmacology of CB-5339

The pharmacodynamics and pharmacokinetic profile of single-dose CB-5339 was determined in RPMI 8226 multiple myeloma (MM) tumor xenografts along with CB-5083 (Figure 8; Pharmacology Report 02-00013). The data demonstrated that CB-5339, like CB-5083, achieved plasma levels sufficient to elicit a pharmacodynamic response specific to p97. The biomarkers modulated in the RPMI 8226 MM model were characteristic of a proteotoxic stress that engaged the tumor in the unfolded protein response pathway and subsequently, triggered the apoptosis of the tumor cells.

[figure not shown]

Figure 8: RPMI8826 multiple myeloma xenografts treated with active doses of CB-5339 (NSC 803952; 110 mg/kg) and CB-5083 (NSC788636; 60 mg/kg) (A) displayed largely similar K48-ub (B), CHOP (C), and cleaved caspase-3 (D) induction. The 110 mg/kg dose of CB-5339 used in the PD studies was not specifically assessed for efficacy, but would, it is presumed, fall within the range of efficacy observed here for 100 mg/kg and 125 mg/kg CB-5339 administered on a QD3/4 off schedule.

CB-5339 exhibited transient peak plasma concentrations in the range of 2.14 to 41 μ M between 1 and 24 hr. CB-5083 plasma concentration ranged from 0.7 to 16.3 μ M during the same interval. Concentrations of p97 inhibitors in tumor lysates generally mirrored the plasmatic concentrations. Dosage of CB-5339 and CB-5083 resulted in time-dependent increases in K48-Ub with peak levels obtained at later time points, past the peak plasma concentrations of the compound. In alignment to what can be observed in sensitive solid tumor models (Le Moigne), significant

increased levels of CHOP protein were observed in the RPMI 8226 MM model, starting at 6 hr, and being sustained up to 10 hr post dosing. Both molecules, CB-5339 and CB- 5083, demonstrated similar induction of CHOP in intensity and durability in this experiment, with ~ 7-10-fold increase between 6 and 10 hr. CHOP is described to be an ER stress marker in the unfolded protein response and has been shown to mediate programmed cell death (Barone et al., 1994). Induction of cPARP, an additional marker of apoptosis, could be detected at the 10-hr time point in the RPMI 8226, with 4.3- fold and 53-fold increases for CB-5339 and CB-5083, respectively.

The tosylate salt form of CB-5339 was selected for clinical development based on higher plasma exposure in dog compared to the free base form of CB-5339.

2.2.4 Preclinical Toxicology of CB-5339 in Rats and Beagle Dogs

Exploratory toxicology studies and IND-enabling studies have been conducted with Sprague-Dawley rats and Beagle dogs. The objectives of the exploratory studies were to determine the maximum tolerated dose MTD and to determine target organs of toxicity and any dose-limiting toxicities. IND-enabling studies were conducted in rats and dogs to estimate the safe starting dose for clinical studies of CB-5339, to further characterize toxic effects with respect to target organs (clinical pathology and histopathology), and to evaluate reversibility of drug effects.

Dose range finding in Beagle dogs: CB-5339

This study evaluated the toxicity and toxicokinetics of CB-5339 in dogs after oral administration daily over two 4-day cycles (Days 1 through 4 and Days 8 through 11, with a 3-day washout period between the two cycles). Doses of CB-5339 were 3.5, 7.5 and 15 mg/kg (de-escalated to 10 mg/kg).

Administration of 3.5 or 7.5 mg/kg/day CB-5339 via oral gavage was tolerated for two 4-day cycles, and a dose level of 10 mg/kg/day was tolerated for one 4-day cycle following a non-tolerated dose of 15 mg/kg/day for 3 days. Administration of 15 mg/kg/day resulted in body weight loss, reduced food consumption, and the moribund condition of one female after three daily doses in Cycle 1. Clinical pathology findings consistent with dehydration, stress/inflammation, and findings secondary to decreased food consumption and body weight were noted for animals administered 15 mg/kg/day. These findings, except the increased cholesterol, were not apparent on Day 12 after lowering the dose to 10 mg/kg/day for the second dosing cycle. Therefore, the maximum-tolerated dose was considered 10 mg/kg/day, which corresponded to Day 11 combined sexes mean C_{max} and AUC_{0-24} values of 702 ng/mL and 3570 ng*hr/mL, respectively. The no-observed-adverse-effect level (NOAEL) was 7.5 mg/kg/day which corresponded to a Day 11 combined sexes mean C_{max} and AUC_{0-24} values of 827 ng/mL and 2090 ng*hr/mL, respectively.

Final Repeat Dose Toxicity and Toxicokinetic Study in Beagle dogs (8376335)

This study evaluated the toxicity and determined the toxicokinetics of CB-5339 when administered via oral gavage to dogs once daily over five 4-day cycles with 3-day washout periods between cycles, and to assess the reversibility or persistence of any effects after a 2-week

recovery phase. The study included an assessment of CB-5339-related effects on ocular structure and function based on slit-lamp biomicroscopy and indirect ophthalmoscopy. Male and female beagles were administered vehicle control article or 3.5, 7.5, or 10 mg/kg/day CB-5339. CB-5339-related clinical pathology effects were limited to minimally decreased red cell distribution width and mildly decreased absolute reticulocyte count in males administered 10 mg/kg/day with no signs of reversibility, except for absolute reticulocyte count in one male. The test article was well tolerated at doses up to 10 mg/kg/day, with no adverse effects. Thus, the NOAEL is 10 mg/kg/day. This dose level corresponded to mean C_{max} and AUC values of 1240 ng/mL and 3080 ng x hr/mL, respectively, in combined sexes on Day 32 of the dosing phase. No significant CB-5339-related clinical observations, alterations in body weight or body weight gain, ocular or electroretinography abnormalities, electrocardiogram abnormalities, or anatomic pathology differences were noted for animals administered up to 10 mg/kg/day.

Dose range finding in Rat: CB-5339

This study evaluated the toxicity and toxicokinetics of CB-5339 when administered via oral gavage to rats daily over five 4-day cycles with 3-day washout periods between cycles. Doses of CB-5339 in female rats were 3, 10, and 30 mg/kg; doses in male rats were 10, 30, and 60 (de-escalated to 40) mg/kg.

Mortality and adverse findings were noted in males administered 60 mg/kg/day and females administered 30 mg/kg/day; the cause of death was marrow hypocellularity and lymphoid depletion/necrosis. Clinical pathology changes included minimally lower reticulocyte count and associated mean corpuscular hemoglobin concentration in males administered \geq 30 mg/kg/day, minimally higher ALT in females administered 30 mg/kg/day and males administered 60/40 mg/kg/day, and mildly lower triglyceride concentration in males administered 60/40 mg/kg/day. These clinical chemistry findings were reversed on Day 15 of the recovery phase. CB-5339-related microscopic findings included moderate marrow hypocellularity, marked pancreas acinar atrophy, and moderate glandular stomach mucosal atrophy in one female administered 30 mg/kg/day, which were considered adverse because of similar microscopic findings noted in animals which were found dead, and slight lymphoid depletion/necrosis in the thymus in females administered 30 mg/kg/day, which were considered adverse because of similar microscopic findings noted in animals which were found dead. Thus, the no observed adverse effect level (NOAEL) is 40 mg/kg/day for males and 10 mg/kg/day for females. These dose levels corresponded to mean C_{max} and AUC values of 696 ng/mL and 5020 ng x hr/mL, respectively, in males and 258 ng/mL and 1070 ng x hr/mL, respectively, in females on Day 32 of the dosing phase.

Final Repeat Dose Toxicity and Toxicokinetic Study in rats (8376333)

This study evaluated the toxicity and determined the toxicokinetics of CB-5339 when administered via oral gavage to rats once daily over five 4-day cycles with 3-day washout periods between cycles, and assessed the reversibility, persistence, or delayed occurrence of any effects after a 2-week recovery phase. Ophthalmic examinations were conducted once during the predose phase for all animals and once for all toxicity animals during Week 5 of the dosing phase

Male rats were administered 10, 30, or 60/40 mg/kg/day CB-5339 and female rats were administered 3, 10, or 30 mg/kg/day CB-5339. Mortality and adverse findings were noted in males administered 60 mg/kg/day and females administered 30 mg/kg/day; microscopic evaluation established the cause of death was marrow hypocellularity and lymphoid depletion/necrosis. Adverse decreases in body weights were observed during the dosing phase for males administered 60 mg/kg/day, following lowering of the dose level to 40 mg/kg/day, the body weight gain recovered. Clinical pathology changes included minimally lower reticulocyte count and associated MCHC in males administered \geq 30 mg/kg/day, minimally higher ALT in females administered 30 mg/kg/day and males administered 60/40 mg/kg/day, and mildly lower triglyceride concentration in males administered 60/40 mg/kg/day. These clinical chemistry findings were reversed on Day 15 of the recovery phase. CB-5339 related microscopic findings included moderate marrow hypocellularity, marked pancreas acinar atrophy, and moderate glandular stomach mucosal atrophy in one female administered 30 mg/kg/day, which were considered adverse because of similar microscopic findings in the animals found dead, and slight lymphoid depletion/necrosis in the thymus in females administered 30 mg/kg/day, again considered adverse because of similar microscopic findings in animals found dead. At the recovery sacrifice, minimal spleen and thymic lymphoid depletion/necrosis was noted in one female administered 30 mg/kg/day, which indicated that recovery of lymphoid findings was in progress, but not yet complete. The remaining findings noted at the terminal sacrifice were resolved. No CB-5339-related ophthalmic findings were noted.

No remarkable ophthalmic observations were noted with the exception of one female (3 mg/kg/day) with multiple foci of retinal hemorrhage in the left eye considered incidental. Effects noted for males administered 40 mg/kg/day and females administered 10 mg/kg/day were considered non-adverse due to the mild severity of findings and the lack of impact on animal health and wellbeing. Thus, the NOAEL is 40 mg/kg/day for males and 10 mg/kg/day for females, confirming the dose-range finding study. These dose levels corresponded to mean Cmax and AUC values of 696 ng/mL and 5020 ng*hr/mL, respectively, in males and 258 ng/mL and 1070 ng*hr/mL, respectively, in females on Day 32 of the dosing phase.

2.2.5 Eye Disorder Studies with CB-5339

Clinical evaluation of Cleave Therapeutics' first-in-class inhibitor of p97, CB-5083 in patients with advanced metastatic solid tumors (NCT02243917) and in lymphoid malignancies (NCT02223598) was halted due to dose-dependent toxicity related to PDE6 inhibition, including grade 2 chromatopsia, grade 2 photophobia, and grade 4 transient loss of vision that improved with drug discontinuation. Reporting rates for at least 1 eye disorder on the solid tumor and lymphoma studies were 25 of 32 subjects (78%) and 5 of 12 subjects (42%), respectively (data from 2016 IB). The median onset was day 1 for the solid tumor trial (range, 1 to 36), 60 to 90 minutes after dosing, and with a median duration of 60 to 120 minutes. Reports for the hematologic study were similar.

In dog toxicology studies with CB-5339 performed for the current proposed study, all animals had a normal ophthalmic and electroretinography (ERG) examinations throughout all phases, except for one male in the dose-ranging study administered 3.5 mg/kg/day, in which the left eye had a

white vitreous floater only at the pre-dose measurement. This was considered an incidental background finding. As noted in Section 2.2.4.2, no CB-5339-related ocular abnormalities were observed on slit-lamp biomicroscopy or indirect ophthalmoscopy during the dosing or recovery phases of the final repeat dose toxicity and toxicokinetic study 8376335.

The pharmacokinetics of CB-5339 and an assessment of its effects on electroretinography (ERG) after a single oral dose to cynomolgus monkeys were measured (Study RPT-02-00032). In brief, three male cynomolgus primates were assigned to each dosing cohort: 10 mg/kg (low), 20 mg/kg (medium) and 40 mg/kg (high). Ophthalmic examinations and intraocular pressure (IOP) measurements were performed predose for all animals. ERG tests were performed predose and at approximately 3 and 24 hours postdose. At the predose ophthalmic examination, all the animals had a normal ophthalmic examination, and the baseline IOP values were within normal limits. CB-5339 was well tolerated, with no adverse clinical observations noted, following a single oral administration to male monkeys at the dose levels administered. The oral administration of CB-5339 at 40 mg/kg did not alter measures of retinal or retinal-cortical function in any of the animals when tested at 3 or 24 hours postdose. All ERG and visual-evoked potential (VEP) tests were within expected limits at baseline and there were no instances of significant depression of the ERG or VEP.

On this current clinical study, an ophthalmology examination including Optical Coherence Tomography (OCT), color vision testing, and a questionnaire will be performed by NEI associate investigators on all patients during screening. The questionnaire will be repeated after treatment on cycle 1 day 1 or 2, and if clinically indicated along with the ophthalmology exam (see [Appendix B](#)).

Characteristic	CB-5083	CB-5339
In vitro biochemical potency (nM)		
PDE6 IC ₅₀ (bovine)	27	380
PDE6 IC ₅₀ (human)	310	3900
In vivo rat tissue distribution		
rat C _{max} retina/plasma ratio	2.5	0.08
rat AUC retina/plasma ratio	4.3	1.1

Figure 9: CB-5339 is 10x less potent on PDE6, has 4x lower retinal penetration and does not cause electroretinographic effects at a similar AUC than CB-5083.

2.2.6 Planned Clinical Dose Levels

Following the ICH S9 guidance (International Council for Harmonisation of Technical Requirements for Pharmaceuticals for Human Use, 2009), we have used the common small molecule approach of setting the first-in-human dose at 1/10th the rodent Severely Toxic Dose in 10% of the animals (STD10). Because male rats required a dose reduction from 60 mg/kg/day to 40 mg/kg/day, while female rats tolerated 30 mg/kg/day without deaths but several adverse findings, we used 30 mg/kg/day as our STD10; dividing this by 10 gives 3 mg/kg/day. This is converted to the human equivalent dose (HED) based on body surface area by dividing the STD10 by 6.2, and is multiplied by 60 for a 60 kg human, to deliver a human starting dose of 29 mg. This dose also aligns well with 1/10th the NOAEL from the most sensitive species, the

beagle dogs, which leads to a human dose of 32 mg. Given the availability of 25 mg capsules for CB-5339 administration, we have set the human starting dose at 25 mg on the 4 days on and 3 days off schedule (dose level -1 will reduce the frequency of administration by 25%). Further dose escalation will reflect one capsule size per dose for patient convenience informed by Fibonacci sequence ([Dose Escalation Table](#)).

PD results from the first 32 subjects on the CLC-101 solid tumor study of CB-5083 indicated that only subjects dosed at 590 mg CB-5083 or higher had measurable increases in K48-Poly-Ub of surrogate tissues (monocytes and B cells) at 2 hours post-dosing. The magnitude of the blood cell K48-Poly-Ub increases seen in these subjects was similar to that seen in the blood of tumor bearing mice and rats indicative of target engagement by CB-5083.

2.2.7 Clinical Trials of CB-5339

CB-5339 is being evaluated in two phase 1 clinical studies. Cleave Therapeutics is sponsoring a phase 1 trial of CB-5339 in patients with relapsed/refractory acute myeloid leukemia or relapsed/refractory intermediate or high risk myelodysplastic syndrome at several sites in the US and Australia ([NCT04402541](#)), and the NCI is conducting this current phase 1 trial in patients with solid tumors and lymphomas. The dosing schedule of once daily, 4 days on and 3 days off, in 28-day cycles, and the starting dose of 25 mg, will be employed in both studies. Both will also employ accelerated dose escalation strategies using single patient dose levels (*this study reverts to standard 3+3 dose escalation as defined in Section 5.2.*).

2.3 Rationale

Based on its well characterized mechanism of action, preclinical data, and experience with Cleave's previous-generation p97 inhibitor, CB-5339 may provide benefits to patients with advanced solid tumors and lymphomas refractory to standard-of-care treatments. The anticancer effects of CB-5339 have been characterized in several *in vitro* and *in vivo* pharmacology studies and an ongoing trial in canine patients, demonstrating that it can elicit a variety of biological effects including induction of an unfolded protein response, decreased cell viability, and apoptosis. The study-objective recommended phase 2 dose (RP2D) will be determined by the following: (1) a dose no higher than the maximum tolerated dose level; (2) obtaining exposures associated with preclinical biomarker activity; and (3) patient responses.

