5.3 Dose Expansion Cohort

Once the RP2D is reached, an additional 15 patients will be treated at this dose to further explore pharmacodynamic endpoints and obtain additional pharmacokinetic data. For the expansion cohort, patients will continue to be monitored for occurrence of toxicities that meet the definition DLT after cycle 1. Once pharmacodynamic data are available, additional expansion cohorts may be considered to explore pharmacodynamic endpoints at lower dose levels (a protocol amendment will be submitted for these changes to the trial design).

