7. BIOMARKER AND CORRELATIVE STUDIES

Blood and urine will be obtained from all patients to determine the PK of CB-5339; BSA additive should be included in the urine collection flask per Section 7.1. Pre- and post-treatment tumor biopsies will be collected on the expansion cohort to measure the effects of CB-5339 on the ubiquitin proteasome system and on markers of cell death; PBMCs will be collected on the escalation cohort as surrogate markers for tumor effect. Blood samples will also be collected for isolation of circulating tumor DNA (ctDNA) as an exploratory endpoint to identify potential genomic biomarkers of response in patients on the expansion cohort.

Record the date, planned time and actual time of collection for each specimen on the PK/PD sample collection sheet

Ophthalmologic Examination will be performed at screening and as clinically indicated.

Ophthalmologic testing and biomicroscopic examinations should include assessment of the following in the order listed whenever possible.

- Best corrected visual acuity (BCVA) using Early Treatment Diabetic Retinopathy Study (ETDRS) methodology. The same methodology is to be used for the pre-study and follow-up examinations for each individual subject.
- Slit lamp examination including assessment of the lids, lashes, conjunctiva, sclera, cornea, anterior chamber, iris, lens and anterior vitreous. The slit lamp examination is repeated following dilation to better assess the lens and anterior vitreous.
- Measurement of intra-ocular pressure.
- Fundus examination. This include assessment of the vitreous, retina, disc, macula, vessels, and periphery of each eye using dilated fundoscopy.
- Spectral domain optical coherence tomography (OCT) of the macula and disc for both eyes. The same type of device is to be used for the pre-study and follow-up examinations for each individual subject.
- Standard field fundus photographs with the pupils dilated performed on each eye to aid in the evaluation of the optic nerve, vessels, macula, and periphery.
- Color vision testing

To be eligible for this research protocol, patients will be screened for pre-existing visual impairment. Patients will be excluded if they do not meet the visual acuity threshold (best corrected visual acuity of 60 ETDRS letters [Snellen equivalent of 20/60] in either eye) and the visual field threshold (substantial visual field loss in one or both eyes).

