APPENDIX C: PD/PK COLLECTION WORKSHEETS

7.1 Pharmacokinetic Analysis

CB-5339 pharmacokinetics will be measured in plasma and urine from all patients during cycle 1 day 1 (the first 3 patients will also have PK blood collected on C1 D4) and during subsequent cycles for patients experiencing toxicity or who have undergone intra-patient dose escalation. A stability additive must be included in urine samples as described below. PK parameters, including area under the plasma concentration versus time curve (AUC), maximum plasma concentration (C_{max}), trough plasma concentration (C_{min}), time to maximum plasma concentration (T_{max}) and plasma terminal elimination half-life ($T_{1/2}$) will be determined using appropriate PK models. PK samples will be batched for analysis at the conclusion of the escalation phase and will not be used to determine escalation or expansion phase doses. *Note: the 8-hr post dose sample collection is optional pending data on agent stability in whole blood overnight until processing.*

One 0.5 mL K₂EDTA tube (pediatric microtainer) will be obtained for each of the time points. The actual time of collection will be noted for each sample, and the sample will be placed immediately on wet ice until processing to plasma.

Blood will be collected at the following times (mandatory all patients except for the 8-hr post dose collection):

- cycle 1 day 1 prior to CB-5339 administration
- cycle 1 day 1 at 15, 30, and 60 minutes, 2hr, 4hr, 6hr, 8hr*, 24hr after CB-5339 (before another dose is taken)

Blood will also be collected at the following times for the first 3 patients only who will be admitted to the Clinical Center until Day 5 (all mandatory except for the 8-hr post dose collection):

- cycle 1 day 4 predose and at 15, 30, and 60 minutes, 2hr, 4hr, 6hr, 8hr*, 24hr after CB-5339 (before another dose is taken)

Patients who have been dose-adjusted will have optional PK samples collected prior to CB-5339 administration on day 1 and then 1, 2, and 24 hours after drug administration (before another dose is taken) during the first cycle following dose adjustment only.

The PK blood tubes/samples should be kept on ice until plasma can be recovered, at which time the plasma samples should be frozen (-70°C). The plasma samples should be stored at -70°C, and shipped to the PK lab at the address below on dry ice.

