- Samples from the first three patients (hospitalized) will be sent in individual batches (i.e., all plasma from the patient's day 1 and 4 collections) for "real-time" PK analysis by validated HPLC-MS/MS. Subsequent patient samples can be stored and batched for shipment (approximately 48 samples/shipment).

A baseline urine collection of 10 mL will be collected just before CB-5339 administration. **1.5% BSA will be added to the sample and mixed well.** Urine will then be collected at

every void from 0 to 24 hours on cycle 1, day 1 for PK analysis. Samples should be placed on wet ice immediately after collection and then refrigerated in the presence of 1.5% BSA. The total volume of urine collected for the 24-hour time period will be documented and a 10-mL sample will be taken from the total volume and saved; the rest can be discarded. PK samples will be shipped to:

Attn: [name]
Alturas Analytics
[name]
[name]
[contact]

Based upon the results of the initial measurements, sampling times may be adjusted but neither the total number of samples nor the total amount of blood will be increased.

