8.3 Analysis of Secondary and Exploratory Endpoints

Once the MTD/RP2D is established, up to 15 additional patients will be enrolled to the expansion phase of the trial. Mandatory tumor biopsies will be obtained in the expansion phase to assess for pharmacodynamic endpoints. With up to 15 patients and a tumor biopsy QA criteria failure rate of 19% with respect to paired (pre- and post-dose) biopsies, we have a 95% likelihood of having at least 10 usable PD paired samples. This will give us at least 90% power to detect a treatment related PD endpoint change of at least 1.8 SDs (with respect to the baseline values of the endpoint) at the 1-sided .01 significance level (to accommodate multiple comparisons).

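### The 6-18 escalation range in Section 8.2, and so the minimum of 21 and maximum of 33 evaluable patients, does not follow from the dose rules in 5.2 and 8.1; a cleared 300 mg level has no MTD or RP2D rule, and one sentence in 2.3 needs aligning.

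*Combined protocol and SAP*

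**What the plan says.** **Sample size.** Section 8.2 gives 6-18 escalation patients and 15 expansion patients, hence 21 as the minimum and 33 as the maximum evaluable. The accrual ceiling is 40, the margin being for patients who are not evaluable. No derivation of 6-18 is given.

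**Dose rules.** Section 5.2 treats one patient per level until the first drug-related grade 2 toxicity in cycle 1, then uses 3+3. It adds three patients after 1 DLT in 3, stops at 2 or more DLTs, and requires at least six patients at the RP2D. The schedule has levels 1-6 (25, 50, 100, 150, 225, 300 mg) and level -1. Section 8.1 defines the MTD as a level with at most 1 DLT in 6 that lies directly below a level with at least 2 DLTs.

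**Expansion.** Section 5.3: "Once the RP2D is reached, an additional 15 patients will be treated at this dose". Section 8.3: "Once the MTD/RP2D is established, up to 15 additional patients will be enrolled to the expansion phase of the trial".

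**Basis of the RP2D.** Section 2.3 sets the MTD as an upper limit and adds "2) obtaining exposures associated with preclinical biomarker activity; and (3) patient responses". Section 7.1 says of the specimens drawn for pharmacokinetics that they "will be batched for analysis at the conclusion of the escalation phase and will not be used to determine escalation or expansion phase doses".

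**The concern.** The RP2D is the primary objective, and the mandatory paired biopsies are all taken at that dose. The patient numbers, the rule that ends escalation and the stated basis of the RP2D should therefore agree.

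The numbers do not. The lower figure of 6 is smaller than the count needed to establish an MTD. The upper figure of 18 leaves no room for three patients at every level plus the six required at the RP2D. If 33 is read as a true maximum, the ceiling of 40 appears to hold 7 spare places (40 - 33) for non-evaluable patients. On several paths that 5.2 allows, those places are used by evaluable patients or do not exist.

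The other two points are smaller. The rules do not say what the MTD or RP2D is if the top level is cleared, and 2.3 lists RP2D criteria that play no part in the dose actually used in expansion.

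**Working it through.** **1. The plan's own figures.** 15 + 6 = 21 and 15 + 18 = 33, so the sums are right. The range 6-18 matches six levels at one patient each (6 x 1 = 6) and at three each (6 x 3 = 18). This match is an inference. Under the rules, an escalation phase of 6 patients arises in two ways:
- all six levels clear with one patient each, which leaves one patient at 300 mg, no MTD, and fewer than the six required at the RP2D;
- the study goes on hold after three patients at level 1 and three at level -1, with no RP2D and no expansion.

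**2. Smallest path to an MTD.** Six patients at the MTD plus two with DLT at the level above: 6 + 2 = 8. If the upper cohort is completed to three: 6 + 3 = 9. Totals are 8 + 15 = 23 and 9 + 15 = 24, against the stated 21. The expansion patients cannot supply the six, because 5.3 makes them additional to a dose already reached.

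**3. Ladder cleared, six patients at 300 mg, no lower level expanded.** If the accelerated phase ends at level j, escalation takes (j - 1) + 3(6 - j) + 6 = 23 - 2j patients.

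| Accelerated phase ends at level | 1 | 2 | 3 | 4 | 5 | 6 |
|---|---|---|---|---|---|---|
| Escalation patients | 21 | 19 | 17 | 15 | 13 | 11 |

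The count exceeds 18 when the phase ends at 25 or 50 mg. Each lower level expanded after 1 DLT in 3 adds three.

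**4. MTD of 225 mg, three per level from level 1, no lower level expanded.** 3 x 4 + 6 + (2 to 6) = 20 to 24.

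**5. Largest paths.** Levels 1-6 with six patients each: 6 x 6 = 36, so 36 + 15 = 51. If de-escalation runs down through level -1: 7 x 6 = 42, so 57. Exhaustive enumeration of outcome paths gave the same limits.

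**6. Against the ceiling.** 40 - 15 = 25 places for escalation. On the cleared ladder with three per level from level 1, the total with m expanded lower levels is 36 + 3m: 36, 39, 42, 45, 48, 51 for m = 0 to 5. The ceiling is passed from m = 2. If the accelerated phase ends at level 2, m = 2 gives 19 + 6 + 15 = 40, with no place for a non-evaluable patient.

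**7. Level 6 cleared.** In 5.2, both 0 DLTs in 3 and 1 in 6 send the trial to the next level, but the schedule ends at 300 mg. The 8.1 MTD needs a level above with at least 2 DLTs. The RP2D row in 5.2 needs a maximally administered dose, which the table declares only when escalation stops for DLTs. That row's gloss, the highest dose given, read literally would point to 225 mg. Section 5 meanwhile continues escalation until the RP2D, equated there with the MTD, is found.

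**8. Basis of the expansion dose.**
- Section 5.2: decisions on dose expansion rest on first-cycle findings.
- Section 5: RP2D and MTD are treated as one.
- Section 8.3: the two terms are joined.
- Section 7.1: PK is excluded from setting expansion doses.

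All four describe a DLT-based expansion dose. Section 2.3 is the only text out of line.

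**The case against.** **On the sample size.** The best defence is that 6-18 is a working estimate. Four of the six counts in step 3 (17, 15, 13, 11) lie within 18. A simulation supports this in part. It assumed DLT rates at 300 mg between 8% and 55%, grade 2 rates mostly one to four times the DLT rate, and 300 mg filled to six. Mean escalation size was 13.5-18.9, P(more than 25) about 0.5%-10%, and P(more than 18) about 15%-57%. The total of 51 on a cleared ladder needs five lower levels each to show 1 in 3 and then 0 in 3. At one level that has probability 3p(1 - p)^5, at most 0.201 (at p = 1/6), so for five about 0.03% at most. This stands as a defence of a planning range and of the ceiling. It does not defend the labels minimum and maximum.

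A reader might infer that the ceiling must rise or that the trial will run out of places. The documents do not support that: 40 covers many paths, and the rest can be handled by amendment.

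**On level 6.** The gap matters only if 300 mg is cleared. The RP2D row says what is generally the case, and investigator sign-off and monthly CTEP calls (12.1) would probably resolve it. That limits the harm without supplying a rule.

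**On 2.3.** A reader might infer that 2.3 and 7.1 together leave the expansion dose undetermined, or that PK should set it. Neither follows. Step 8 shows that the dose is settled by DLTs, and the exclusion of PK is an explicit design choice. The early PK exception ("Samples from the first three patients (hospitalized) will be sent in individual batches") covers at most 25, 50 and 100 mg and has no stated dose role. Nor has the PBMC work: "PBMCs will be collected on the escalation cohort as surrogate markers for tumor effect". The exposure evidence gives no usable threshold: "CB-5339 exhibited transient peak plasma concentrations in the range of 2.14 to 41" micromolar is a roughly 19-fold span (41 / 2.14) in a single-dose mouse xenograft study. The plan also leaves room for later revision: "Once pharmacodynamic data are available, additional expansion cohorts may be considered to explore pharmacodynamic endpoints at lower dose levels", by amendment, and 12.2.2 records the RP2D at study end.

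**Conclusion.** The main point holds as an error in the text. The 8.2 figures are not the minimum and maximum under 5.2 and 8.1. The rule-based bounds for paths that reach an MTD, or clear 300 mg with six patients there, are 8-36 escalation patients on levels 1-6 and 23-51 in total (9 and 24 at the lower end with full cohorts of three). Through level -1 the upper limits are 42 and 57. These bounds need no assumption about DLT rates, and no probability is claimed for any single path.

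The level 6 gap is real but contingent and secondary. The 2.3 mismatch is one of wording and does not put the dose-finding method in doubt. Together these should be fixed; none invalidates a safety rule or an analysis.

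**What to change.** **Section 8.2 (main).** Either state the bounds above, or keep 6-18 as a planning range and remove the words minimum and maximum from 21 and 33. In both cases add that the ceiling of 40 leaves 25 places for escalation, and that paths needing more, or needing those places for non-evaluable patients, require an amendment. The ceiling need not be raised, so the accrual period and enrolment table can stay. Cost: wording only.

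**Sections 5.2 and 8.1, with the Section 5 sentence on when escalation ends (secondary).** State that if level 6 is cleared, at least six patients are treated there. With at most 1 DLT in 6, the MTD is reported as not reached and 300 mg is the highest dose eligible as RP2D, unless levels are added by amendment. Cost: none if level 6 clears at 1 in 6, three more patients if it clears at 0 in 3, five if it clears with a single patient. Where patients are added, accrual takes 3/2 = 1.5 to 5/1 = 5 months at 1-2 per month. With one 28-day cycle (0.92 month) that is about 2.4 to 5.9 months. The existing minimum of six at the RP2D already implies these patients.

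**Section 2.3 (wording).** State that the expansion dose is the DLT-based MTD, or the highest cleared dose, and that the final RP2D is confirmed at study end using PK and response. Section 7.1 can stay as it is. Cost: none.
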